## **8.4. Human Antihuman Antibodies**

The formation of antibodies to patritumab will be characterized by a screening test for HAHA and, if positive, a confirmatory test to determine antibody titers. If antibody titers indicate HAHA to patritumab are present, then the sample will be assayed to determine whether antibodies are neutralizing.

Blood samples will be collected within 3 days prior to Day 1 of Cycle 1 (baseline), Cycle 2 (preinfusion), Cycle 3 (preinfusion), and at End of Study Treatment visit. For subjects with positive HAHA at the End of Study Treatment visit, additional serum HAHA and PK samples should be collected every 3 months up to 1 year from the last dose of study

drug or if the subject starts another therapy for cancer, or withdraws consent from the study, whichever occurs first. Detection of HAHA formation in serum samples will be performed using validated assays.

For instructions on management of HAHA samples please refer to the laboratory manual.

## **8.5. Pharmacogenomics**

Blood samples will be collected for pharmacogenetic sample banking from subjects who have provided a separate informed consent for this part of the study as an exploratory objective (Section 2.1.3). Participation in this part of the study is optional for all subjects. For those subjects who choose to participate, samples will be banked for possible future pharmacogenetic and germ-line DNA analysis. These samples may be analyzed only for genes suspected to contribute to the safety and efficacy of the study medications.

Samples will be retained until the DNA has been exhausted or until the Sponsor instructs the genotyping contractor to destroy the sample (in accordance with laboratory procedures). During the period of storage, the DNA sample will not be immortalized or sold to anyone. Subjects will have the right to withdraw consent and have their sample destroyed at any time.

For instructions on management of pharmacogenomics, please refer to the laboratory manual.

## **9. SAFETY ASSESSMENTS**

### **9.1. Adverse Events**

All clinical AEs occurring after the subject signs the Informed Consent Form for general study participation and up to 40 days after the last dose of any study drug administered, whether observed by the investigator or reported by the subject, will be recorded on the Adverse Event CRF page. Medical conditions (including laboratory values/vital signs that are out of range) that were diagnosed or known to exist prior to Informed Consent will be recorded as part of medical history.

All AEs, SAEs, and events of special interest are to be reported according to the procedures in Section 9.5.

Any laboratory findings should be appraised by the investigator as to clinical significance. An isolated abnormal laboratory result (ie, not related to a reported diagnosis) should be reported as an AE if it is symptomatic, leads to study drug reduction or discontinuation, requires corrective treatment, or is defined as an AE of Special Interest in Section 9.3.

At each visit, the investigator will determine whether any AEs have occurred by evaluating the subject. Adverse events may be directly observed, reported spontaneously by the subject or by questioning the subject at each study visit. Subjects should be questioned in a general way, without asking about the occurrence of any specific symptoms. The Investigator must assess all AEs to determine seriousness, severity, and causality, in accordance with the definitions in Section 9.4. The Investigator's assessment must be clearly documented in the site's source documentation with the Investigator's signature.

Always report the diagnosis as an AE or SAE term. When a diagnosis is unavailable, report the primary sign or symptom as the AE or SAE term with additional details included in the narrative until the diagnosis becomes available. If the signs and symptoms are distinct and do not suggest a common diagnosis, report them as individual entries of AE or SAE. For events that are serious due to hospitalization, the reason for hospitalization must be reported as the SAE (diagnosis or symptom requiring hospitalization). A procedure is not an AE or SAE, but the reason for the procedure may be an AE or SAE. Pre-planned (prior to signing the Informed Consent Form) procedure or treatment requiring hospitalization for pre-existing conditions which do not worsen in severity should not be reported as SAEs (see Section 9.4 for Definitions).

For deaths, the underlying or immediate cause of death should always be reported as an SAE. Disease progression is a study endpoint and consequently, should not be reported as an AE/SAE. However, when a subject dies from disease progression with no other immediate causes, "disease progression" should be reported as an SAE on the Serious Adverse Event Report (SAVER) form (see Section 9.5) and recorded on the patient outcome eCRF. In addition, any serious, untoward event that may occur subsequent to the reporting period that the Investigator assesses as related to study drug should also be reported and managed as an SAE.

The Investigator should follow subjects with AEs until the event has resolved or the condition has stabilized. In case of unresolved AEs, including significant abnormal laboratory values at the end of study assessment, these events will be followed until resolution or until they become clinically not relevant.

## **9.2. Safety Endpoints**

Not applicable

## **9.3. Events of Special Interest**

### **9.3.1. Combined Elevations of Aminotransferases and Bilirubin**

Combined elevations of aminotransferases and bilirubin, either serious or non-serious and whether or not causally related, meeting the criteria of a potential Hy's Law case (ALT or AST  $\geq 3 \times$  ULN with simultaneous total bilirubin level  $> 2 \times$  ULN) should always be reported to the Sponsor using a SAVER form with the investigator's assessment of seriousness, causality, and a detailed narrative. In addition, an eCRF for liver toxicity should be completed (See Section 9.5).

If the subject discontinues study drug due to liver enzyme abnormalities, the subject will be followed until the abnormality resolves or is considered stable.

### **9.3.2. Interstitial Lung Disease**

In a subject who develops an acute onset of new or progressive pulmonary symptoms, such as dyspnea, cough or fever, study treatment should be interrupted pending diagnostic evaluation. If interstitial lung disease (ILD) is diagnosed by the Investigator, the subject should be treated immediately and permanently discontinued from study treatment. Information relevant to safety reporting of ILD will be captured on the eCRF.

## **9.4. Definitions**

### **9.4.1. Adverse Event**

An AE is any untoward medical occurrence in a patient, or clinical investigation subject administered a pharmaceutical product and which does not necessarily have a causal relationship with this treatment. An AE can, therefore, be any unfavorable and unintended sign (including an abnormal laboratory finding, for example), symptom, or disease temporally associated with the use of a medicinal product, whether or not considered related to the medicinal product.

It is the responsibility of Investigators, based on their knowledge and experience, to determine those circumstances or abnormal laboratory findings which should be considered AEs.

### **9.4.2. Serious Adverse Event**

Any untoward medical occurrence that at any dose:

- Results in death

- Is life-threatening
- Requires inpatient hospitalization or prolongation of existing hospitalization
- Results in persistent or significant disability/incapacity
- Is a congenital anomaly/birth defect, or
- Is an important medical event

Note: The term “life-threatening” in the definition of “serious” refers to an event in which the subject was at risk of death at the time of the event; it does not refer to an event which hypothetically might have caused death if it were more severe.

Medical and scientific judgment should be exercised in deciding whether expedited reporting is appropriate in other situations, such as important medical events that may not be immediately life-threatening or result in death or hospitalization but may jeopardize the subject or may require intervention to prevent one of the other outcomes listed in the definition above. Examples include allergic bronchospasm, convulsions, and blood dyscrasias, or development of drug dependency or drug abuse.

Note:

- A procedure is not an AE or SAE, but the reason for the procedure may be an AE or SAE
- Pre-planned (prior to signing the Informed Consent Form) procedures or treatment requiring hospitalizations for pre-existing conditions which do not worsen in severity are not SAEs

#### **9.4.3. AE Severity**

The following definitions should be used to assess intensity of AEs according to the latest NCI CTCAE:

- Grade 1 Mild: Awareness of sign or symptom, but easily tolerated, ie, does not interfere with subject’s usual function
- Grade 2 Moderate: Discomfort enough to cause interference with usual activity
- Grade 3 Severe: Incapacitating with inability to work or do usual activity, ie, interferes significantly with subject’s usual functions
- Grade 4: Life-threatening consequences; urgent intervention indicated
- Grade 5: Death related to AE

The NCI CTCAE guidelines do not allow certain grades for certain AEs. For example, pain can be Grade 1 to 3 only (ie, cannot be life-threatening or fatal), whereas sepsis can only be Grade 4 or 5 (ie, can only be life-threatening or fatal). In addition, alopecia can only be Grade 1 or 2. The NCI CTCAE guidelines should be followed closely.

Severity vs. Seriousness: Severity is used to describe the intensity of a specific event, while the event itself, however, may be of relatively minor medical significance (such as

severe headache). This is not the same as "seriousness," which is based on patient/event outcome at the time of the event. For example, the NCI CTCAE Grade 4 (life-threatening consequences; urgent intervention indicated, or disabling) is assessed based on unique clinical descriptions of severity for each AE, and these criteria may be different from those used for the assessment of AE seriousness. An AE assessed as Grade 4 based on the NCI CTCAE grades may or may not be assessed as serious based on the seriousness criteria.

#### **9.4.4. Causality Assessment**

The investigator should assess causal relationship between an AE and each of the study drugs on the basis of his/her clinical judgment and the following definitions. The causality assessment should be made based on the available information and can be updated as new information becomes available.

- 1 = Related:
  - The AE follows a reasonable temporal sequence from study drug administration, and cannot be reasonably explained by the subject's clinical state or other factors (eg, disease under study, concurrent diseases, and concomitant medications)
  - The AE follows a reasonable temporal sequence from study drug administration, and is a known reaction to the drug under study or its chemical group, or is predicted by known pharmacology
- 2 = Not Related:
  - The AE does not follow a reasonable sequence from study product administration, or can be reasonably explained by the subject's clinical state or other factors (eg, disease under study, concurrent diseases, and concomitant medications)

#### **9.4.5. Action Taken Regarding the Study Product**

- 1 = Dose Not Changed: No change in study drug dosage was made
- 2 = Drug Withdrawn: The study product was permanently stopped
- 3 = Dose Reduced: The dosage of study product was reduced
- 4 = Drug Interrupted: The study product was temporarily stopped

#### **9.4.6. Adverse Event Outcome**

- 1 = Recovered/Resolved
  - The subject fully recovered from the AE with no residual effect observed
- 2 = Recovered/Resolved with Sequelae
  - The residual effects of the AE are still present and observable
  - Include sequelae/residual effects

- 3 = Not Recovered/Not Resolved
  - The AE itself is still present and observable
- 4 = Fatal
- 5 = Unknown

#### **9.4.7. Other Action Taken for Event**

- 1 = None
  - No treatment was required
- 2 = Medication required
  - Prescription and/or over-the-counter medication was required to treat the AE
- 3 = Other

### **9.5. Safety Reporting – Procedure for Investigators**

All AEs, SAEs, and events of special interest will be reported in the eCRF. In addition, the Investigator should report the following types of events on a SAVER form within 24 hours of becoming aware of them:

- SAEs (see Section 9.4.2)
- Hepatic events, both serious and nonserious, presenting with combination abnormalities meeting criteria for a potential “Hy’s law” case (ie, ALT or AST  $\geq 3 \times$  ULN, with simultaneous total bilirubin  $> 2 \times$  ULN; see Section 9.3.1)

All events (serious and nonserious) must be reported with the Investigator’s assessment of the event’s seriousness, severity, and causal relationship to study drug. A detailed narrative summarizing the course of the event, including its evaluation, treatment, and outcome should be provided. Specific or estimated dates of event onset, treatment, and resolution should be included when available. Medical history, concomitant medications, and laboratory data that are relevant to the event should also be summarized in the narrative. For fatal events, the narrative should state whether an autopsy was or will be performed, and should include the results if available. Source documents will be retained in site’s files and should not be submitted to the Sponsor for SAE reporting purposes.

Urgent safety queries must be followed up and addressed promptly. Follow-up information and response to non-urgent safety queries should be combined for reporting to provide the most complete data possible within each follow-up.

Please call the local SAE Hotline number (Section 15.2.1.5) or your study monitor for any questions on SAE reporting.

### **9.5.1. Notifying Regulatory Authorities, Investigators, and IRBs/IECs**

Daiichi Sankyo and/or CRO will inform Investigators, IRBs/IECs, and regulatory authorities of any Suspected Unexpected Serious Adverse Event Reactions occurring in other study centers or other Daiichi Sankyo studies of the investigational product, as appropriate per local reporting requirements.

## **9.6. Exposure In Utero During Clinical Studies**

Daiichi Sankyo must be notified of any subject who becomes pregnant while receiving or within 40 days of discontinuing the investigational product. Although pregnancy is not technically an AE, all pregnancies must be followed to conclusion to determine their outcome. This information is important for both drug safety and public health concerns. It is the responsibility of the Investigator, or designee, to report any pregnancy in a female subject using the Exposure In Utero Reporting form. Please contact your study monitor to receive the Exposure In Utero Reporting Form upon learning of a pregnancy. The Investigator should make every effort to follow the subject until completion of the pregnancy. If the outcome of the pregnancy meets the criteria for immediate classification as a SAE (ie, post-partum complications, spontaneous abortion, stillbirth, neonatal death, or congenital anomaly, including that in an aborted fetus), the Investigator should follow the procedures for reporting SAEs outlined in Section 9.5.

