  12. Adult subjects of child-bearing potential must agree to use double-barrier contraceptive measures. Two of the following precautions must be used: bilateral vasectomy, bilateral tubal ligation, intrauterine device (IUD), combined (estrogen and progesterone containing) hormonal contraception associated with inhibition of ovulation (oral, intravaginal, transdermal), progesterone-only hormonal contraception associated with inhibition of ovulation (oral, injectable, implantable), intrauterine hormone-releasing system (IUS), condom with spermicide, abstinence. These contraception measures must be used for the entire duration of the study and for 6 months after the last study dose is received
  13. Subjects must be willing and able to comply with schedule visits, treatment plan, laboratory tests, and other study procedures
  14. Provided written informed consent(s)

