#### **4.1.1. Inclusion Criteria**

Subjects must satisfy all of the following criteria to be included in the study:

1. Adult subjects  $\geq 18$  years old
2. Histologically confirmed recurrent disease or metastatic SCCHN tumor and/or from its lymph nodal metastases originating from the oral cavity, oropharynx, hypopharynx, and larynx
3. Heregulin expression level is required
  - Samples must be taken from subjects who have recurrent or metastatic disease (rec/met). These samples can be from either rec/met archived or fresh biopsy samples (either primary tumor or metastases)
  - No cancer treatment between time of biopsy and submission of sample
  - Surgical or core needle biopsy is acceptable
  - Fine-needle aspiration or cytology is not acceptable for biopsies
4. HPV status or p16 (surrogate for HPV) is required. These results must come from tumor tissue. These results may be obtained from either a local lab or samples sent to the central lab
  - HPV or p16 status can be from any tumor biopsy material from initial diagnosis
5. Measurable disease per Response Evaluation Criteria in Solid Tumor (RECIST) Version 1.1

6. Eastern Cooperative Oncology Group (ECOG) performance status 0 or 1
7. Hematological function, as follows:
  - Absolute neutrophil count (ANC)  $\geq 1.5 \times 10^9/L$
  - Platelet count  $\geq 100 \times 10^9/L$
  - Hemoglobin  $\geq 10$  g/dL
8. Renal function, as follows:
  - Estimated serum creatinine clearance (mL/min) or GFR  $\geq 60$  mL/min for cisplatin and  $\geq 30$  mL/min for carboplatin
9. Hepatic function, as follows:
  - Aspartate aminotransferase (AST)  $\leq 2.5$  x upper limit of normal (ULN) (if liver metastases are present,  $< 5$  x ULN)
  - Alanine aminotransferase (ALT)  $\leq 2.5$  x ULN (if liver metastases are present,  $< 5$  x ULN)
  - Alkaline phosphatase  $\leq 2.0$  x ULN (if bone or liver metastases are present,  $< 5$  x ULN)
  - Bilirubin  $\leq 1.5$  x ULN
10. Prothrombin time or partial thromboplastin time  $\leq 1.5$  x ULN
11. Women of childbearing potential must have a negative serum pregnancy test performed within 14 days prior to enrollment (where demanded by local regulations, test may be required within 72 hours prior to enrollment)

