12. Adult subjects of child-bearing potential must agree to use double-barrier contraceptive measures. Two of the following precautions must be used: bilateral vasectomy, bilateral tubal ligation, intrauterine device (IUD), combined (estrogen and progesterone containing) hormonal contraception associated with inhibition of ovulation (oral, intravaginal, transdermal), progesterone-only hormonal contraception associated with inhibition of ovulation (oral, injectable, implantable), intrauterine hormone-releasing system (IUS), condom with spermicide, abstinence. These contraception measures must be used for the entire duration of the study and for 6 months after the last study dose is received
13. Subjects must be willing and able to comply with scheduled visits, treatment plan, laboratory tests, and other study procedures
14. Provided written informed consent(s)

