## **5. TREATMENTS ADMINISTERED**

### **5.1. Investigational Products**

The Investigator must ensure that the blinded investigational product (ie, patritumab) will be used only in accordance with the protocol, as specified in Section 3.1.2. Placebo will be provided in a matching vial.

The vial labels will contain a description of the contents, batch number, and where appropriate, storage conditions and any additional statements as required by local regulations.

Daiichi Sankyo will provide carboplatin for this study. Wherever possible, commercial supplies of cetuximab and cisplatin will be supplied by the clinical site.

Daiichi Sankyo will only supply cetuximab and cisplatin to those sites that are not able to supply themselves.

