#### 6.1.2. Screening (Up to 14 Days Before the First Dose of Study Treatment Unless Otherwise Noted)

Screening procedures can be done at the same time as tissue screening (Section 6.1.1) at the discretion of the Investigator.

The following activities and/or assessments will be performed at/during screening (within 14 days before the first dose of study treatment [unless otherwise noted]):

- Obtain signed informed consent
- Obtain signed informed consent for pharmacogenomics (optional)
- Evaluation of inclusion and exclusion criteria
- Confirm results of the HRG expression level and HPV or p16 status.
- Record demographic and medical history information
  - Including smoking history

- Record AEs and concomitant medications
- Perform a physical examination, including vital sign measurements, blood pressure, heart rate, temperature, weight, and height. Height will be measured only at Screening
- Assess functional status using the ECOG Performance Status Scale (Section 10.1)
- Perform an echocardiogram or multigated acquisition (MUGA) scan (the same test must be used for a subject throughout the study) (Section 9.11.1)
- Perform a 12-lead ECG
- Collect blood sample for complete blood count (CBC) (Section 9.7)
- Collect blood sample for coagulation-only at Screening (Section 9.7)
- Collect blood sample for serum chemistry (Section 9.7)
- Obtain urine sample for urinalysis (Section 9.7)
- Perform a serum or urine pregnancy test for female subjects of childbearing potential (must be confirmed negative before dosing). Additional pregnancy testing may be done at the discretion of the Investigator and/or if required by local regulations for women of child-bearing potential (Section 9.7)
- Perform radiographic tumor assessments after eligibility is determined. Existing radiographic scans can be used for the baseline evaluation if the scans were performed within 4 weeks prior to randomization. Computed tomography (CT) and/or magnetic resonance imaging (MRI) (spiral CT or MRI with  $\leq 5$  mm cuts) should be used for tumor assessment unless another modality of radiographic disease assessment is necessary for the lesions per RECIST guidelines Version 1.1, (see Appendix 17.3)

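### Section 9.6 states a 40-day pregnancy notification window while inclusion 12 requires contraception for 6 months after the last study dose; about 78% of that period lies outside the stated window, and the clocks start from different events.

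*Protocol*

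**What the plan says.** **Notification.** Protocol Section 9.6 requires the sponsor to be told of "any subject who becomes pregnant while receiving or within 40 days of discontinuing the investigational product". Section 5.1 identifies this product as "the blinded investigational product (ie, patritumab", with matching placebo; cetuximab and platinum are not part of it. Section 9.6 also makes the investigator or designee responsible "to report any pregnancy in a female subject using the Exposure In Utero Reporting form" and says every pregnancy is to be followed to its outcome. Neither of those statements carries a time limit.

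**Contraception.** Inclusion 12 in Protocol Section 4.1.1 reads: "These contraception measures must be used for the entire duration of the study and for 6 months after the last study dose is received". The protocol synopsis and the SAP synopsis repeat the 6 months.

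**Adverse events.** Section 9.1 collects events "up to 40 days after the last dose of any study drug administered". This is the same number of days as in Section 9.6, but counted from a different event.

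**Screening test.** Inclusion 11 states: "Women of childbearing potential must have a negative serum pregnancy test performed within 14 days prior to enrollment". Section 6.1.2 instructs sites: "Perform a serum or urine pregnancy test for female subjects of childbearing potential (must be confirmed negative before dosing".

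**The concern.** The protocol asks subjects to avoid pregnancy for 6 months after the last study dose, but the only dated duty to notify the sponsor ends much sooner and is counted from one component of the regimen. Section 9.6 itself calls this information important for drug safety and public health. A site that reads the dated sentence as the rule could treat a pregnancy conceived in month 3 as not notifiable. A site that reads the undated sentence could report it. Capture of late exposures would then depend on how each site reads the section, and on whether the site hears of the pregnancy at all.

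The screening mismatch is smaller. A site working from the Section 6.1.2 list may perform a urine test and then find that inclusion 11 has not been met.

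**Working it through.** The plan gives the two periods but no comparison of them, so there is no stated figure to reproduce.

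**Inputs**
- Stated notification window: 40 days (Protocol 9.6).
- Contraception period after treatment: 6 months (inclusion 12), taken as *D* = 180 to 184 days. The day count is an assumption.
- *s* = days from the last patritumab/placebo dose to the last study dose. Patritumab/placebo is given on Day 1 of each 21-day cycle and cetuximab on Days 1, 8 and 15 (Sections 3.1.2.1, 6.2.4 and 6.2.5; Table 17.2), so *s* = 0, 7 or 14 when treatment stops within one cycle.
- Discontinuing is dated from the last patritumab/placebo infusion. Section 9.6 does not define that date, so this is also an assumption.

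**Formula**

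Uncovered days = *D* − (40 − *s*); uncovered share = uncovered days / *D*.

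| *s* | *D* = 180 | *D* = 183 | *D* = 184 |
|---|---|---|---|
| 0 | 140/180 = 77.8% | 143/183 = 78.1% | 144/184 = 78.3% |
| 7 | 147/180 = 81.7% | 150/183 = 82.0% | 151/184 = 82.1% |
| 14 | 154/180 = 85.6% | 157/183 = 85.8% | 158/184 = 85.9% |

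If discontinuation were instead dated at the next missed infusion, 21 days later, the window would reach 40 + 21 = 61 days. The uncovered share at *s* = 0 would be (183 − 61)/183 = 122/183 = 66.7%, still most of the period.

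**Contacts that could reveal a pregnancy after treatment**
- End of Study Treatment visit, 21 days after the last dose (6.2.9): the last scheduled pregnancy test.
- Call at 40 days after the last dose of any study drug (6.2.10): records adverse events. Section 9.6 says a pregnancy is not technically an adverse event.
- Calls about every 3 months thereafter (6.3): survival information.
- Some subjects also have later tumor assessments or antibody samples. No pregnancy test or question is attached to them.

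**Screening test, side by side**
- Inclusion 11: serum.
- Section 6.1.2: serum or urine.
- Section 9.7: serum or urine, with no visit named.
- Table 17.2, footnote m: no specimen named.

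Only the first two conflict directly. The SAP shell for Listing 16.2.4.2 shows a screening result by urine, so the planned output also anticipates urine tests.

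**The case against.** The strongest answer is that Section 9.6 is wider than its dated sentence. It asks for any pregnancy in a female subject to be reported, tells sites to request the form when they learn of a pregnancy, and wants every pregnancy followed to its end. Section 9.1 also brings in later serious events that the investigator judges related to study drug. A reader might infer that pregnancies after day 40 would go unreported; the documents do not support that. This part of the objection stands. What remains is one dated window, undated sentences that can be read more widely, and nothing scheduled to find a late pregnancy.

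A second answer is that a contraception period and a reporting period need not be equal. Inclusion 12 cites external contraception guidance, and the protocol never calls the 6 months a risk or exposure period. This also stands: the difference alone does not show that 40 days is wrong. It does call for a stated reason, and none is given.

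A third tempting inference is that a subject could stop patritumab/placebo, continue the other drugs for a long time, and become pregnant on treatment outside the rule. Section 5.1.7 says that a subject who must discontinue patritumab/placebo is withdrawn from the study. A general sentence in the same section has subjects continue on the drugs they tolerate, so the text is in tension, but it does not establish the scenario. The 7- to 14-day offset needs only the normal weekly cetuximab schedule.

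Finally, a reader might infer that following Section 6.1.2 lets a woman be randomized without meeting inclusion 11. The same screening list requires the eligibility criteria to be checked, Section 4.1.1 requires all of them to be met, and Section 6.4 allows no waiver except for an immediate hazard. The mismatch invites deviations; it does not authorize them.

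**Conclusion.** The point holds as an inconsistency in safety reporting. About 78% of the required post-treatment contraception period lies outside the only stated notification window when both clocks start together, and about 82% to 86% when the last cetuximab dose follows the last patritumab/placebo dose by 7 to 14 days. This rests on 6 months being 180 to 184 days and on discontinuation being dated from the last infusion; dated 21 days later, the share is about 67%.

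These are shares of calendar days, not of pregnancies. The documents give no expected number of women of childbearing potential, so the number of affected exposures cannot be estimated. The documents also do not show which duration is right; they show that the passages must be reconciled or the difference explained. The screening-test mismatch is real but minor. Neither point touches the PFS endpoint, randomization or power.

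**What to change.** 1. Reconcile Section 9.6 with inclusion 12: run the notification window from the last dose of any study drug through the end of the required contraception period, or keep a shorter window and state the reason. Say in the same paragraph whether the duty to report any pregnancy is bounded by that window.
2. Add a pregnancy question to the 3-monthly survival calls (Section 6.3) that fall within the period, roughly two per subject. Table 17.3 lists no survival calls for the extension phase, so name the contact at which the question will be asked there.
3. Make inclusion 11 and the Section 6.1.2 bullet name the same screening test, and check that Section 9.7 does not read against it.

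The cost is protocol wording and one question on calls already planned. The downside is a slightly longer notification duty for sites. No analysis changes.
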